8.3. Sample Size Determination

The study will enroll approximately 390 subjects. In two Phase 3 clinical trials with adalimumab (PIONEER I and II; [Kimball et al, 2016a](#)), the proportions of subjects in the placebo control group achieving a HiSCR at Week 12 were 26.0% and 27.6%, respectively. Hence, if the control group only receives placebo, one may assume a HiSCR at Week 12 of approximately 30%. The average HiSCR at Week 12 in the adalimumab groups in PIONEER I and II were 41.8% and 58.9%, respectively with an average of approximately 50% ([Kimball et al, 2016a](#)). The attrition rate throughout the trial is estimated to be approximately 7%. A sample size of approximately 130 subjects per treatment group (390 in total) at a Type I error rate of $\alpha = 0.05$ (two-sided) provides approximately 90% power to detect a 20% superiority of avacopan compared to the placebo control group in HiSCR at Week 12, assuming an HiSCR at Week 12 of 50% in the avacopan group.

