8.4. Analysis Populations

8.4.1. Modified Intent-to-Treat Population

For the purposes of efficacy data analysis, the Modified Intent-to-Treat (mITT) population will be used. This population will include all subjects who are randomized and received at least one dose of study drug. The efficacy population will be analyzed according to the treatment group each subject is randomized to. The mITT population will be the primary analysis population for the efficacy analysis.

The mITT populations are defined for the two treatment periods as the following:

- The mITT1 Population in Period 1 is defined as all subjects who are randomized at baseline and have received at least one dose of study drug during Period 1.
- The mITT2 Population in Period 2 is defined as all subjects who have received at least one dose of study drug during Period 2.

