8.8. Statistical Analysis Methodology

8.8.1. General Approach

All study data will be summarized by treatment using descriptive statistics. Categorical variables will be reported as frequency and percent (e.g., gender, race). Continuous variables will be reported as number of subjects, mean, standard deviation, median, minimum, and maximum (e.g., age, weight). All summaries, statistical analyses, and individual subject data listings described below will be completed using Version 9.3 or later of the SAS Statistical Analysis System (SAS Institute, Inc. Cary, NC).

All statistical testing will be two-sided, with the Type I error rate at $\alpha = 0.05$.

Baseline is defined as the last value prior to start of dosing with study drug (typically the Day 1 pre-dose value).

Non-Responder Analysis: For non-responder analysis, the following imputation rules will be applied to categorical and continuous efficacy variables, respectively:

- Categorical Efficacy Variables: Non-Responder Imputation (NRI) will be used as the primary analysis. Last Observation Carried Forward (LOCF) will be the secondary approach for the non-responder analysis.
- Continuous Efficacy Variables: LOCF will be used as the primary analysis. The valid assessments from last visit prior to the visit the subject was considered a non-responder will be carried forward to the end of study for continuous efficacy variables. Baseline efficacy evaluations will not be carried forward.

The following are examples for subjects who will be counted as non-responder:

- Concomitant anti-TNF- α treatment or other treatments with clinically relevant impact on HS;
- Antibiotic rescue therapy;
- Non-protocol specified lesion intervention, or higher than permitted frequency or number of pre-specified lesion interventions. Protocol-specified lesion interventions will *not* be counted as Non-responder.

Concomitant therapy that would qualify a subject as non-responder will be reviewed prior to database lock. More details will be provided in the Statistical Analysis Plan (SAP).

Missing Data Analysis: For missing data analysis, the following imputation rules will be applied to categorical and continuous efficacy variables, respectively:

- Categorical Efficacy Variables: NRI will be the primary approach for categorical variables. The NRI analysis will count subjects who have missing values at a specific visit as non-responders for that visit. LOCF will be the secondary approach for the missing data analysis.

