8.8.2. Analysis of Primary Efficacy Endpoint

The primary efficacy endpoint, the proportion of subjects achieving HiSCR at Week 12 will be tested using the Cochran-Mantel-Haenszel (CMH) test, stratified by Hurley Stage (Stage II vs. III), concomitant antibiotic therapy with allowed antibiotics (Yes vs. No) and anti-TNF drug use (Treatment naïve vs. Previous treatment). The hierarchical testing procedure will be used for the comparisons of the 10 mg avacopan vs. placebo and 30 mg avacopan vs. placebo to maintain the overall Type I error at 0.05. The 30 mg avacopan vs. placebo will be tested first: if the p-value is less than or equal to 0.05, then 10 mg avacopan vs. placebo will be tested at the $\alpha = 0.05$ level. If the test of avacopan 30 mg vs. placebo is not significant at the $\alpha = 0.05$ level, the 10 mg avacopan vs. placebo will be tested as an exploratory analysis. The two-sided 95% confidence intervals for the difference in proportions (avacopan minus placebo control) will be calculated using the stratified Newcombe hybrid-score method. The primary efficacy analysis will be carried out in the mITT1 Population. In addition, the primary efficacy endpoint will be analyzed in the Per-Protocol Population.

The proportion of subjects achieving HiSCR at Week 12 will be calculated as those subjects having at least a 50% reduction from baseline in abscess and inflammatory nodule count, with no increase in abscess count and no increase in draining fistula count number at Week 12 divided by the total number of subjects randomized to the particular treatment group.

8.8.3. Analysis of Secondary and Other Efficacy Endpoints in Period 1

The Secondary and Other Efficacy Endpoints for Period 1 will be tested separately for the 10 mg and 30 mg avacopan groups at Type I error at 0.05. The analyses will be carried out in the mITT1 Population. Analysis of other efficacy endpoints will be conducted from Day 1 to each timepoint.

Categorical variables of change from Day 1 to Week 12 will be analyzed using CMH test stratified for baseline Hurley Stage (Stage II vs. III), concomitant antibiotic therapy with allowed antibiotics (Yes vs. No) and anti-TNF- α drug use (Treatment naïve vs. Previous treatment) similar to the analysis of the primary efficacy endpoint.

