For secondary efficacy endpoint testing, the avacopan 30 mg vs. placebo or the avacopan 10 mg vs. placebo will be tested separately with the $\alpha = 0.05$ level, provided that the corresponding primary endpoint testing of the same dose level is significant. As the two drug doses are two independent families, and the outcome of the study is to select one dose, not 2 doses. A fixed hierarchical testing sequence will be employed, as following:

H₂: Change from Baseline in total AN count at Week 12

H₃: NRS30 at Week 12

H₄: % subjects with baseline Hurley Stage II who achieved AN count of 0, 1, or 2 at Week 12

H₅: Reduction of IHS4 at Week 12

H₆: Change from Baseline in inflammatory nodule count at Week 12

H₇: Change from Baseline in abscess count at Week 12

H₈: Change from Baseline in draining fistula count at Week 12

H₉: Change from Baseline in Modified Sartorius score at Week 12

Comparisons involving other efficacy endpoints and time points are considered supportive or exploratory and will be made at α =0.050 level (two-sided). No multiplicity adjustment will be made for these comparisons.

J. Analysis Populations

Analysis populations will be defined for use with various analyses.

Intent-to-Treat Population

The Intent-to-Treat (ITT) Population will include all subjects who are randomized and have received at least one dose of study drug, and who are not from study Site 138. Subjects from Site 138 will be excluded from the ITT Population due to potential misconduct and non-compliance at site 138.

The ITT populations are defined for the two treatment periods as the following:

- The ITT1 Population in Period 1 is defined as all subjects who are randomized at baseline and have received at least one dose of study drug during Period 1.
- The ITT2 Population in Period 2 is defined as all subjects who have received at least one dose of study drug during Period 2.

Per Protocol Population

The per protocol (PP) population for period 1 will consist of ITT1 and do not have protocol deviations that could significantly affect the interpretation of the results for the primary endpoints. Subjects' inclusion/exclusion from the PP population will be determined and documented prior to the database lock and unblinding.

Per-Protocol Population in Period 1 (PP1) will include subjects in ITT1 who meet all the following criteria:

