- Receive at least 70% of the planned study drug in Period 1 for subjects who complete Period 1 or receive at least one dose of study drug and discontinue Period 1
- Provide at least one post Baseline assessment on lesion count
- Meet the Hurly stage II: Total SCAR and Fistula counts > 0 at either screening or Day 1.
- Have Baseline AN count ≥ 3
- Have Baseline draining fistula count ≤ 20
- Do not take the following exclusionary medications during the exclusionary screening period or during Period 1:
- Any concomitant antibiotics for the treatment of HS (except the protocol allowed rescue medication which will result in counting the subjects as non-responders, or having the last observation prior to the use of these treatments carried forward).
- Anti-TNF-a (Humira), Methotrexate (MTX), cyclosporin, corticosteroids, and retinoids for any reason, or other medication for treatment of their HS that will confound the efficacy evaluation (to be determined and documented in the classification results prior to blind break).

Per-Protocol Population in Period 2 (PP2) will be defined separately.

Subjects included in the Per-Protocol Population will be analyzed as treated. That is, if a subject receives the treatment that is not the randomized assignment during their entire participation of a period, the subject will be analyzed according to the treatment that the subject actually received in the period.

Safety Population

The Safety Population will include all subjects who are randomized and have received at least one dose of study drug, excluding those subjects who are from study Site 138. Due to the reasons stated above safety data of subjects from site 138, including adverse events, will be listed separately only and not be included in the summary tables:

- The Safety Population in Period 1 (Safety1) is defined as all subjects who are randomized at baseline and have received at least one dose of study drug during Period 1.
- The Safety Population in Period 2 (Safety2) is defined as all subjects who
 received at least one dose of avacopan during Period 2.
- The All Avacopan Treated Population is defined as all subjects who receive at least one dose of avacopan in any treatment period.

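### Site 138 is excluded from efficacy and from all safety summary tables, and no planned analysis shows the results with it included

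*SAP*

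**What the plan says.** Protocol section 8.4.1 sets the primary efficacy population (mITT): "This population will include all subjects who are randomized and received at least one dose of study drug". Section 8.4.3 defines the safety populations in the same inclusive way. Neither has a site exclusion.

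SAP section VI.J renames the efficacy population ITT and narrows it: "Subjects from Site 138 will be excluded from the ITT Population due to potential misconduct and non-compliance at site 138". For the Safety Population it says that "safety data of subjects from site 138, including adverse events, will be listed separately only and not be included in the summary tables". Section I.A states that SAP definitions supersede the protocol's, so this rule governs. Section X shows the protocol and SAP definitions side by side, so the change is disclosed.

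The populations that the SAP then uses are these:
- Primary HiSCR analysis, its three sensitivity analyses and the subgroup analyses (VIII.D): ITT1.
- Per-protocol analysis: PP1, a subset of ITT1 (VI.J).
- COVID-19 sensitivity analysis (IX.I): ITT.
- Safety tables (IX): the Safety Population.
- Pharmacokinetics: subsets of the safety populations (VI.J).

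No efficacy analysis or safety summary adds Site 138 back.

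**The concern.** Subjects at Site 138 were randomised and dosed, and are then removed as a block on a ground that the SAP itself calls only potential. The usual way to show that such an exclusion does not drive the conclusion is to report the result with and without the site. This plan produces only the result without it.

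Two things are at stake. For efficacy, the 30 mg comparison is tested first and opens both the 10 mg comparison and the 30 mg secondary endpoints (SAP VI.I), so a borderline change there spreads through the hierarchy. For safety, comparison with placebo is a primary objective (Protocol 2.1). A serious event in a dosed Site 138 subject would be in a listing, but in neither the numerator nor the denominator of any incidence. Doubt about a site's conduct does not change the fact that its subjects were exposed.

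**Working it through.** **Inputs.** Protocol 8.3: 130 per arm; placebo HiSCR ("one may assume a HiSCR at Week 12 of approximately 30" per cent); avacopan HiSCR 50%; attrition about 7%. Two-sided testing (8.8.1: "All statistical testing will be two-sided") at 0.05 (8.8.2). The size of Site 138 is not given, so a range is used, split equally over the three arms.

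**1. Reproduce the plan's power.** The protocol says that this sample size "provides approximately 90% power to detect a 20% superiority of avacopan compared to the placebo control group". With a pooled-variance normal approximation,

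power = Φ{ [0.20 − 1.96·√(2·0.40·0.60/n)] / √[(0.30·0.70 + 0.50·0.50)/n] }.

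At n = 130: (0.20 − 1.96 × 0.0608)/0.0595 = 1.36, so power is 91.3%. At n = 121 (130 × 0.93) it is 89.3%. Both agree with approximately 90%.

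**2. Power after removing the site**, n = 130 − k/3 per arm:

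| Subjects removed in total (k) | Power |
|---|---|
| 0 | 91.3% |
| 8 | 90.7% |
| 16 | 90.2% |
| 24 | 89.5% |
| 39 | 88.2% |

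Starting from 121 per arm, removing 39 subjects takes 89.3% to 85.6%. Power is not the main problem.

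**3. How far an arm's rate can move.** Remove 5 of 130, of whom r are responders; the new rate is (x − r)/125.
- 30% arm (x = 39): r = 5 gives 34/125 = 27.2%, a shift of 2.8 points; r = 0 gives 39/125 = 31.2%, a shift of 1.2.
- 50% arm (x = 65): r = 5 gives 60/125 = 48.0% and r = 0 gives 65/125 = 52.0%, a shift of 2.0 either way.

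The most that the difference between arms can move is 2.8 + 2.0 = 4.8 points.

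**4. Can that change a conclusion?** Illustration with an unstratified pooled z test (the planned test is a stratified CMH):
- All subjects: 39/130 against 54/130. The difference is 0.1154, pooled rate 93/260 = 0.3577, SE 0.0595, z = 1.94, p = 0.052.
- Remove 5 per arm, with 2 responders in each, so that the site shows no treatment difference: 37/125 against 52/125. The difference is 0.120, pooled rate 89/250 = 0.356, SE 0.0606, z = 1.98, p = 0.048.

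A site of 5 per arm can therefore carry a borderline result across 0.05. The counts were chosen to lie near the boundary; they show that it can happen, not that it is likely.

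**The case against.** The strongest defence has four parts.

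- **The change is open.** Section X sets it out with its reason, and SAP I.A requires revisions to the primary endpoint analyses to be made before the Week 12 database freeze. This stands as disclosure, but it does not show what the exclusion does to the result.
- **Safety data are not hidden.** Site 138 events are listed separately, and an external DMC reviews data unblinded during the study (Protocol 5.4 and 10.1.6). This also stands. It would be wrong to say that the events disappear; what is missing is their place in any incidence.
- **The exclusion is by site, across all arms.** It does not pick subjects by outcome or assigned arm, and if the data are unreliable, a result that includes them does not settle which answer is right. This is a fair reason to keep the exclusion as the main analysis. It is not a reason to omit the comparison.
- **Site size is unknown.** The importance of the exclusion cannot be fixed from the documents. That is correct, and it limits the size of the claim.

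A reader might also infer that the rules conflict, because the period bullets do not repeat the exclusion: "The ITT1 Population in Period 1 is defined as all subjects who are randomized at baseline and have received at least one dose", with no mention of the site. The documents do not support that. The ITT1 and ITT2 bullets are introduced as period versions of a parent population that excludes Site 138. The Safety1, Safety2 and All Avacopan Treated bullets follow directly from the sentence that excludes it. The natural reading is inheritance. If ITT1 did include the site, the primary, sensitivity and PP1 analyses would include it too, and the present concern would not arise for efficacy.

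**Conclusion.** The concern holds as a gap in robustness and in safety reporting. As written, the trial cannot show whether its primary result, or its adverse event incidence, depends on leaving out Site 138.

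The size is modest and conditional. Power falls by about 3 points (91.3% to 88.2%) even if 39 of 390 subjects go. With 5 removed per arm, the shift is at most 2.8 points in a 30% arm and 2.0 points in a 50% arm, which matters only when the test is close. These figures assume the protocol's planning rates and an equal split of the site over the arms; the true site size is not in the documents.

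Nothing in the documents shows that the exclusion was chosen for its effect on the result, that it biases the comparison, or that keeping the site in would be more correct. The silence of the period bullets is editorial only.

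**What to change.** Keep the exclusion as the main analysis if wanted, and add to the SAP:

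1. A supplementary primary HiSCR analysis in all randomised and dosed subjects including Site 138 (the protocol's mITT1), with the same CMH test, confidence interval and non-responder imputation.
2. Adverse event, serious adverse event and special-interest event summary tables on all dosed subjects including Site 138, labelled as such and showing how many subjects per arm come from that site.

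As an editorial change, state the exclusion in the ITT1, ITT2, Safety1, Safety2 and All Avacopan Treated bullets.

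The cost is one more efficacy table, a few more safety tables and a few words. The downside is that data from a doubted site are shown, which the labels address. The hierarchy and the main analysis do not change.

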Continuous variables will be analyzed using a mixed effects model for repeated measures. This model will include treatment group, visit, treatment-by-visit interaction, and randomization strata (Hurley Stage II or Hurley Stage III, previous anti-TNF- α drug use or anti-TNF- α drug naïve, concomitant antibiotic therapy use or not) as factors, and baseline as covariate. Subjects will be considered as repeated measure units over visits. Testing p-values, point estimates and corresponding 95% confidence intervals will be estimated for the difference between the

avacopan group and the placebo control group across 12 weeks using linear contrast from the model.

For the analysis of subject's global assessment of skin pain (NRS30) up to Week 12, subjects who received analgesics or disallowed pain therapy will be counted as non-responder for categorical variables. For continuous variables, LOCF applies. Hereby, the last pain assessment is carried forward from the start day of the analgesics or day of the intervention until 14 days after the stop of analgesic use or day of the intervention. Concomitant medication for treatment of pain will be reviewed. Disallowed pain therapy will be determined by a blinded data review prior to database lock.

The test of 10 mg vs. 30 mg avacopan groups will be conducted at each timepoint for the endpoint of the proportion of subjects achieving HiSCR and the secondary endpoints. A detailed Type I management plan for the secondary endpoint testing will be provided in SAP.

8.8.4. Analysis of Secondary and Other Efficacy Endpoints in Period 2

The efficacy data for secondary and other endpoints by timepoint in Period 2 will be summarized using the mITT2 population. Analysis of other efficacy endpoints will be conducted from Day 1 to each timepoint.

For the analysis of time to loss of response (LOR), the treatment difference between the 10 mg and 30 mg avacopan groups will be analyzed using the stratified log-rank test with baseline randomization stratification factors as the stratification variables.

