- Change from Baseline in inflammatory nodule count at Week 12.
- Change from Baseline in abscess count at Week 12.
- Change from Baseline in draining fistula count at Week 12.
- Change from Baseline to Week 12 in the modified Sartorius score to quantify the severity change of HS;

Other Efficacy Endpoints

The following efficacy endpoints will be analyzed from Baseline to each timepoint up to Week 44, where applicable:

- Proportion of subjects achieving HiSCR, HiSCR₇₅, and HiSCR₉₀;
- Proportion of subjects achieving at least 30% reduction and at least 1 unit reduction from Baseline in the subject's global assessment of skin pain (NRS30), in subjects with a Baseline NRS of at least 3;
- Proportion of subjects with baseline Hurley Stage II who achieved an abscess and inflammatory nodule count of 0, 1, or 2;
- Change from Baseline in inflammatory nodule count, abscess count, non-inflammatory count, draining fistula, non-draining fistula, total fistula count, and total AN count;
- % Change from Baseline in inflammatory nodule count, abscess count, noninflammatory count, draining fistula, non-draining fistula, total fistula count, and total AN count among subjects who have at least one corresponding lesion at Baseline;
- Change from Baseline in the Sartorius score, modified Sartorius score, IHS4 score, and HS-PGA to quantify the severity change of HS;
- Change from Baseline in subject-reported outcomes: SF-36 v2, EQ-5D-5L, HiSQOL and DLQI;

- Proportion of subjects who experienced flare, defined by at least a 25% increase in AN counts with a minimum increase of 2 AN lesions relative to Baseline;
- Duration of flare in days (calculated from the day when flare is observed to the day
 prior to the observation that flare is no longer present; of note, there could be multiple
 periods that flares are observed, in which case, the total days from the multiple periods
 will be used);
- Proportion of subjects who experience at least 25% increase in draining fistula counts with a minimum increase of 2 draining fistula counts relative to Baseline;
- During Period 2, proportion of subjects with a loss of response, (LOR) defined as loss of at least 50% of AN count improvement achieved from Week 12 in Period 1;
- 12. Time to LOR during Period 2;
- 13. Proportion of subjects who received add-on antibiotic or other therapy during Period 1 and Period 2 including the follow-up period separately;

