- Follow-up Period (8 weeks)

Subjects will be screened for eligibility based on the stage of the disease and their health status. The screening period will be up to 28 days. The primary efficacy analysis will occur when the last enrolled subject has completed the Week 12 visit. After the blinded 12-week treatment period, all subjects will continue an additional 24-week treatment with either 10 mg or 30 mg avacopan twice daily. The treatment assignment to 10 mg or 30 mg twice daily will not be disclosed to the subject, study personnel at the site or the sponsor. Thereafter, all subjects will be followed for 8 weeks.

B. Study Population

Eligible adult subjects (at least 18 years of age) with moderate to severe hidradenitis suppurativa (Hurley stage II or III) on standard-of-care therapy as specified by the inclusion and exclusion criteria in the protocol Section 4, are allowed to enter the study.

C. Sample Size Estimation

The study will enroll approximately 390 subjects. In two Phase 3 clinical trials with adalimumab (PIONEER I and II; Kimball et al, 2016a), the proportions of subjects in the placebo control group achieving a HiSCR at Week 12 were 26.0% and 27.6%, respectively. Hence, if the control group only receives placebo, one may assume an HiSCR at Week 12 of approximately 30%. The average HiSCR at Week 12 in the adalimumab groups in PIONEER I and II were 41.8% and 58.9%, respectively with an average of approximately 50% (Kimball et al, 2016a). The attrition rate throughout the trial is estimated to be approximately 7%. A sample size of approximately 130 subjects per treatment group (390 in total) at a type I error rate of $\alpha = 0.05$ (two-sided) provides approximately 90% power to detect a 20% superiority of avacopan compared to the placebo control group in HiSCR at Week 12, assuming an HiSCR at Week 12 of 50% in the avacopan group.

D. Treatment Randomization

[figure not shown]
Subjects will be randomized 1:1:1 to one of the three treatment groups within each stratum based on a non-dynamic, list-based blocked randomization scheme

receive 10 mg avacopan twice daily, 30 mg avacopan twice daily or matching placebo for 12 weeks in a double-blind, placebo-controlled manner stratified by:

- 1) Hurley stage (Stage II vs III)
- 2) Concomitant antibiotic therapy (Yes vs No)
- 3) Anti-TNF-α treatment (Treatment naive vs Previous treatment)

E. Assessment Schedule

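### Period 2 efficacy is summarised only in subjects who took a Period 2 dose, so later response rates in the two avacopan arms omit early leavers and drug stoppers and can be biased upward

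*SAP*

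**What the plan says.** SAP III.A sets out HiSCR and the other responder endpoints as one series that "will be analyzed from Baseline to each timepoint up to Week 44, where applicable". Efficacy from Day 1 through Week 44 is also a stated objective (Protocol 2.2, SAP II.B).

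The population changes partway through that series:

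- **Period 1.** SAP VIII.E analyses secondary and other endpoints in ITT1, meaning subjects randomised and dosed in Period 1.
- **Period 2.** SAP VIII.E uses ITT2, which SAP VI.J defines thus: "The ITT2 Population in Period 2 is defined as all subjects who have received at least one dose of study drug during Period 2". Protocol 8.8.4 makes the same choice: "The efficacy data for secondary and other endpoints by timepoint in Period 2 will be summarized using the mITT2 population".
- **Denominator.** Under SAP VI.L, percentages are taken over the size of the analysis population concerned.
- **Missing binary data.** Non-responder imputation (NRI) applies in both periods (SAP VI.C, VIII.E), but in Period 2 only within ITT2.
- **Visit windows.** SAP VI.B counts Period 2 study days from the first Period 2 dose.

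Protocol 4.4 asks sites to keep following subjects who stop study drug and to complete their efficacy assessments. Protocol 5.7 requires drug to be stopped after more than two lesion interventions in the first 12 weeks, and asks those subjects to stay in the study. Neither document plans a Period 2 summary on the ITT1 denominator.

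**The concern.** Taking a Period 2 dose is a post-randomisation event. A subject in the 10 mg or 30 mg arm who leaves, or stops drug, before that dose is in the Week 12 denominator and out of the Week 16 denominator. If Week 12 is missing, NRI scores the subject as a non-responder at Week 12, and that non-responder is then removed.

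Subjects followed off drug are lost to the Period 2 summaries as well. Without a Period 2 dose they are outside ITT2 and have no Period 2 study day, so their Week 16 to Week 44 lesion counts reach the listings only. The protocol goes to some trouble to collect those counts.

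Two readings of the Period 2 tables are at stake. One is whether response is maintained or improves after Week 12. The other is how 10 mg and 30 mg compare over time, in a trial whose outcome, according to SAP VI.I, is to choose one dose. If entry to Period 2 differs between the arms, their later rates no longer compare the groups formed by randomisation at Day 1.

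**Working it through.** **Inputs.** SAP IV.C gives about 130 subjects per arm, a 30% placebo rate, the avacopan rate ("assuming an HiSCR at Week 12 of 50% in the avacopan group") and about 7% attrition over the whole trial. No attrition figure for Period 1 alone is given, so its timing has to be assumed.

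**The plan's own figure.** SAP IV.C says the sample size "provides approximately 90% power to detect a 20% superiority of avacopan". The pooled-variance normal approximation is

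power = Φ{[d√n − 1.96√(2p̄(1−p̄))] / √(p₁(1−p₁) + p₂(1−p₂))},

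with d = 0.20, p̄ = 0.40, p₁ = 0.30, p₂ = 0.50.

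- n = 130: (2.280 − 1.358)/0.678 = 1.360, power 91.3%.
- n = 121 (130 less 7%): (2.200 − 1.358)/0.678 = 1.242, power 89.3%.

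Both agree with about 90%, so 130 per arm and 50% are sound working values. The documents give no figure for the change of denominator itself.

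**General form.** Let p be the arm's rate on the ITT1 denominator, a the fraction excluded from ITT2, and q the response rate among those excluded. The ITT2 rate is (p − aq)/(1 − a), and the bias is a(p − q)/(1 − a). It is positive whenever q < p, zero at q = p and negative when q > p.

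**Size at q = 0.** This is the largest bias for a given number excluded. It assumes 130 per arm, the same responders at Weeks 12 and 16, and every excluded subject a non-responder.

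| Excluded before a Period 2 dose | At 50%: ITT1 to ITT2 | Bias | At 30%: bias |
|---|---|---|---|
| 2 (7% × 12/44 = 1.9%; evenly spread) | 65/130 = 50.0% to 65/128 = 50.8% | +0.8 | +0.5 |
| 9 (all of the 7%) | 50.0% to 65/121 = 53.7% | +3.7 | +2.2 |
| 13 (10%, assumed) | 50.0% to 65/117 = 55.6% | +5.6 | +3.3 |
| 20 (15%, assumed) | 50.0% to 65/110 = 59.1% | +9.1 | +5.5 |

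The last two rows apply only if drug stoppers who remain in follow-up come on top of the 7%. They are upper bounds, because such subjects are scored on observed counts when they attend and some may be responders.

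**When the rate does not rise.** With 9 excluded, 4 of them responders, the ITT2 rate is 61/121 = 50.4%. With 5 responders it is 60/121 = 49.6%. If none of the 9 responded but 5 continuing responders lose response by Week 16, the ITT2 rate is again 60/121 = 49.6%. On the ITT1 denominator it would be 60/130 = 46.2%. In that last case the table shows no rise, yet the ITT2 rate is still 3.4 points too high.

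**Unequal entry (illustration).** If both arms have 65 responders of 130 and exclude 2 and 9 non-responders respectively, ITT2 shows 50.8% against 53.7%. That is an apparent dose difference of 2.9 points where none exists.

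**The case against.** A reader might infer that everyone who failed in Period 1 disappears and that response must therefore rise at Week 16. The documents do not support this.

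- Protocol 4.4 lets all subjects enter Period 2 unless safety, the Investigator's judgement or withdrawn consent prevents it. An ordinary HiSCR non-responder who continues drug stays in ITT2.
- Stopping drug is not in itself non-response. A stopper who attends Week 12 is scored on actual counts, unless a separate rule, such as the one for disallowed treatment, applies.
- The rise is conditional, as the working shows.

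Three further defences carry weight. First, SAP VIII presents Period 1 and Period 2 tables separately, and Period 2 responder data are descriptive, so no continuous curve across Week 12 is specified. Second, the only planned Period 2 test of 30 mg against 10 mg is time to loss of response, an endpoint defined from Period 2 onward, and SAP VI.I treats such comparisons as supportive or exploratory. Third, the disposition and analysis-population tables (SAP VII.A) will show how many subjects were lost, and all measurements appear in listings.

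These points limit the consequence. They do not supply a Week 16 to Week 44 estimate for the groups as randomised. Separate tables for one endpoint series still invite comparison across Week 12, and a disposition table does not show what the rates would be on the full denominator.

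**Conclusion.** The concern holds in limited form. For the two arms randomised to avacopan at Day 1, responder rates after Week 12 are conditional on taking a Period 2 dose. They are biased upward whenever those excluded responded less often than the arm. That direction is plausible, since the excluded include early leavers imputed as non-responders and subjects taken off drug for excess lesion interventions, but it is not certain.

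At a 50% rate and the planned 7% attrition, the bias lies between about +0.8 points (evenly spread over 44 weeks) and about +3.7 points (all in Period 1). A larger figure needs the unsupported assumption that drug stoppers still in follow-up add materially to the exclusions. A distorted dose comparison requires entry to differ by arm, which the documents neither show nor rule out.

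The Week 12 primary analysis and the ranked secondary tests use ITT1 and are unaffected. The change is worth making because it is cheap and uses data already being collected.

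**What to change.** For the arms randomised to 10 mg and 30 mg at Day 1, add by-visit summaries of HiSCR and the other binary responder endpoints through Week 44 in ITT1 with NRI. Use observed lesion counts from subjects followed off drug.

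For subjects with no Period 2 dose, assign visits by study day from the Day 1 first dose. The rule must say where Week 12 ends for them, because SAP VI.B Table 1 lets the Week 12 window run as late as Day 114 while the Week 16 visit is scheduled for Day 113.

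Keep ITT2 as a supplementary population for these two arms and as the population for the placebo-to-avacopan groups. Footnote the ITT2 tables to say that the denominator changes after Week 12 and how many subjects per arm are left out.

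The cost is one more set of tables, one added windowing rule and its programming, and probably slightly less favourable long-term rates. No new data are needed and the primary analysis does not change.
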